In a study similar to that of Walmrath (above), Domenighetti (Domenighetti 2001) also titrated Flolan for optimum oxygenation using an ultrasonic nebulized added to the inspiratory arm of the ventilator. In this study, subjects were separated by their etiology; ARDS originating from pulmonary versus extrapulmonary disease. Patients were considered responders if PGI₂ increased PaO_{2 \geq} 7.5 torr or PaO₂/FiO₂ increased \geq 10%. Eight of the nine subjects with ARDS secondary to pulmonary disease responded, whereas none of the ARDS subjects defined by a pulmonary insult responded. In the pulmonary group, PaO₂/FiO₂ decreased from 146± 16 to 135 ± 17, and PaO₂ decreased from 87 to 79. Hemodynamic and other gas exchange variables (mean systemic arterial pressure, cardiac index, oxygen delivery, total systemic resistance, mean right atrial pressure, mixed venous blood gas) were minimally affected.

The effect of Flolan on the PaO_2/FiO_2 ratio is in contrast to the results reported by Walmrath, although in their study subjects were not subset by etiology of the ARDS. One possible explanation is that the pulmonary ARDS subjects in the study reported by Domenighetti had significantly lower mean CT density scores (HU) than the non-pulmonary group indicating more consolidation of the lung and may represent more severe lung pathology. Walmrath had previously demonstrated that aerosolized Flolan was effective in improving gas exchange in

patients with acute respiratory failure linked to pneumonia (Walmrath 1995) suggesting that the etiology may not be the only cause of the lack of response in the Domenighetti study.

Aerosolized lloprost was studied in 20 patients with ARDS and PH (PA > 25 mm Hg). The mean PaO_2/FiO_2 at baseline was 191. The dose of lloprost was 10 μ g administered in 1 ml of saline over 5 minutes for an estimated dose delivered to the lung of 2.5 μ g. A second dose of 20 μ g was administered 30 minutes after the first dose. Iloprost increased PaO_2 from 82 to 100 mm Hg which lasted for 2 hours. Only 4 subjects increase $PaO_2 > 10$ mm Hg following the second dose. PaO_2/FiO_2 also improved. There were no significant changes in systemic hemodynamics.

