Analysis of covariance (ANCOVA) will be used to compare trends for the primary outcome PaO₂/FiO₂ ratio between days 0 and 7 between intervention and control patients. PaO₂/FiO₂ ratio is measured at baseline (day 0), and days 2, 7,. The difference in treatment groups for change from baseline to day 7 and days 2 will be estimated using an ANCOVA adjusting for baseline value. 95% and 80% confidence intervals for the difference in least squares means will be calculated. Due to small sample sizes, substantial normality departures due to skewness will be assessed. As a supportive exploratory analysis, if a number of patients do not have a day 7 assessment, a mixed linear model for repeated measures (MMRM) of PaO₂/FiO₂ ratio at days 0, 2, and 7 will be explored. The focus of the analysis is to assess preliminary evidence of efficacy. Sample size permitting, trends will be evaluated separately in trauma and non-trauma patients.

The secondary efficacy outcome, 28 day ventilator free days, is defined as days alive and free of mechanical ventilation during the first 28 days after randomization. Patients who die will receive 0 ventilator free days. Patients who are discharged free of mechanical ventilation prior to day 28 will be assumed to remain free of mechanical ventilation unless they are readmitted. Ventilator free days is expected to be skewed. Comparisons between treatment groups will focus on 95% and 80% confidence intervals of the Hodges-Lehman estimator for location shift.

Time until mechanical ventilation and time until death will be described via Kaplan-Meier survival curves.

Remaining efficacy outcomes and biomarkers will be analyzed with similar methods. Categorical outcomes will be characterized by odds ratios and assessed with chi-squared tests or Fisher's exact tests. Biomarker values change from baseline will be assessed comparing treatment groups overall and stratified by whether the acute lung injury was resolved by day 28.

Sample size calculation

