Sample size calculations are based on simple t tests. Assuming a change in PaO_2/FiO_2 ratio of 15 in the intervention group and 10 in controls, a standard deviation of 6 (effect size of 0.833), and power of 0.80, the study would require 34 patients in the intervention group and 17 patients in the control group for a 2-sided test with significance level p < 0.05. While we will not approach these numbers, they serve to provide a framework as to the sample size needed to observe clinically meaningful changes in oxygenation as statistically significant. This current proposal centers on safety and feasibility, and thus does not meet the statistical criteria needed to observe minimally significant changes in oxygenation. The planned sample size of 30 total participants has 80% power to produce a 2-sided 80% confidence interval with lower confidence limit above 0 if the true effect size is 0.833.

Twenty-eight day ventilator-free days is a continuous variable. The mean 28 day ventilator free

Version: 02-09-2018

days for the control group of the most recent ARDS network trial was 15 days (95% CI 14.1 – 15.9). The patients enrolled for this trial will have significantly more ventilator free days as a number of them will not require mechanical ventilation at all. A study with 100 patients would have a power of 0.8 to show a 3 day difference in 28 day ventilator free days assuming a value of 22 for controls and 25 for intervention patients, with a SD of 5 days. Since this is an initial, smaller feasibility and proof of concept trial, we will not be able to obtain this level of statistical rigor.

Study feasibility will be assessed by enrollment rate over the first 6 months of the study. If the enrollment rate at that time suggests high feasibility such that the enrollment target of 30 patients can be exceeded easily within the funded enrollment period, we will consider amending the protocol to enroll a small number of additional subjects. This will be discussed and reviewed by the study DSMB. [name], Department of Biostatistics, UNC will provide statistical support.

Part 3. Data Collection and Site Monitoring

Data Collection

Research coordinators will collect data and enter it directly into a computer-based data entry system managed by the TRACS institute or on paper data forms.

Site Monitoring

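### Does the unsourced SD of 6 for change in PaO2/FiO2 undermine the 30- and 51-patient figures?

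*Combined protocol and SAP*

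**What the plan says.** In Sample size calculation, the plan uses simple t tests and assumes a change in PaO2/FiO2 "ratio of 15 in the intervention group and 10 in controls", with "a standard deviation of 6 (effect size of 0.833), and power of 0.80". At two-sided 0.05 and 2:1 allocation this gives 34 active and 17 control patients. The plan says it will not come near that total and describes the figures this way: "they serve to provide a framework as to the sample size needed to observe clinically meaningful changes in oxygenation as statistically significant". It then says that the trial centres on safety and feasibility and does not meet the statistical criteria for oxygenation. The closing statement is that the planned 30 patients "has 80% power to produce a 2-sided 80% confidence interval with lower confidence limit above 0 if the true effect size is 0.833".

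Under Efficacy, the treatment difference in change "will be estimated using an ANCOVA adjusting for baseline value", with 95% and 80% confidence intervals and a check for skewness.

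No citation, pilot data or rationale accompanies the SD. The only PaO2/FiO2 spread printed anywhere is in the background, for one subgroup of a small nebulised-prostacyclin study, where the ratio "decreased from 146± 16 to 135 ± 17". The ± is not defined.

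**The concern.** The primary endpoint is change in PaO2/FiO2, and the effect size of 0.833 is simply 5 divided by 6. If the true SD of change is well above 6, then 51 patients are far too few to detect 5 mmHg, and 30 patients have much less than an 80% chance of an 80% interval above 0.

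There is reason to suspect a larger SD. The blood gases are single spot samples at day 0, day 2 and day 7 in acutely ill patients, and FiO2 is read from a table of fixed steps (Appendix 3). The background spread of 16 to 17 is almost three times the assumed SD.

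At stake is how the paragraph is read. Someone could take the 80% figure as power for 5 mmHg, or carry 51 forward as the size of the next trial.

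**Working it through.** **Inputs.** Difference 15 − 10 = 5, SD 6, two-sided 0.05, power 0.80, 2:1 allocation, N = 30 split 20:10 (Sample size calculation; Study Design). Spread 16 and 17 (background). All SDs other than 6, and all correlations, are assumptions.

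**Reproducing the plan.**
- Control n = (1 + 1/2) × (1.96 + 0.8416)² × (6/5)² = 1.5 × 7.849 × 1.44 = 16.95, so 17 + 34 = 51. This matches. Under the noncentral t, 51 patients have 78.5% power and 54 are needed for 80%, a trivial difference.
- With 20:10, effect size 0.833 and a two-sided 80% interval, the noncentral t gives 0.799. This matches.

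**Dependence on the SD, difference held at 5 mmHg.**

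| Assumed SD | Total N, two-sided 0.05 (normal formula) | Power of 34+17 | Chance of 80% CI above 0, 20:10 |
|---|---|---|---|
| 6 | 51 | 0.79 | 0.80 |
| 8 | 93 | 0.54 | 0.62 |
| 10 | 144 | 0.38 | 0.50 |
| 20 | 567 | 0.13 | 0.26 |

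The last column would be 0.10 with no effect. In SD units the 30-patient design does not depend on the table. The 80% interval half-width is t(0.90, 28 df) × √(1/20 + 1/10) × SD = 1.31 × 0.387 × SD = 0.51 × SD. The difference with 80% power is about 0.83 × SD.

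**What the background spread implies.** If 16 and 17 are SDs, the SD of change is √(16² + 17² − 2r × 16 × 17).
- Setting this to 6 gives r = (256 + 289 − 36)/544 = 0.936.
- r = 0.9 / 0.8 / 0.5 gives 7.4 / 10.5 / 16.5.
- Baseline adjustment does not alter the picture. The residual SD 17 × √(1 − r²) is 7.4 / 10.2 / 14.7 at the same correlations, and reaching 6 again needs r of about 0.94.
- If the ± values are standard errors, the required r is higher still.

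**Two other checks.**
- *Ventilator-free days.* The same section plans that outcome "assuming a value of 22 for controls and 25 for intervention patients, with a SD of 5 days". Let D = 28 − ventilator-free days in controls, with mean 6 and SD 5. Then P(D > 0) ≥ 6²/(6² + 5²) = 36/61 = 0.59. From the mean alone the bound is 6/28 = 0.21. With mean change 10 and SD 6, the one-sided Chebyshev bound allows at most 36/(36 + 100) = 0.26 of controls to show no gain. The 0.59 looks hard to square with the 0.26. But it depends on another unsourced SD, and the outcome "is defined as days alive and free of mechanical ventilation during the first 28 days after randomization", whereas the last PaO2/FiO2 is at day 7. On the mean alone, 0.21 lies below 0.26 and there is no conflict.
- *Room air.* One patient in 30 moving from 4 LPM (FiO2 0.36) to room air, at an assumed PaO2 of 60, gains 60/0.21 − 60/0.36 = 119. With the other 29 unchanged, the SD is 119/√30 = 21.7. This shows sensitivity to one outlier and is not an estimate of the expected SD. Appendix 2 also takes the ratio only while the patient is in hospital, so such a patient may have no day 7 value.

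**The case for a change.** The best case for a change is that figures offered as a framework should show how far they depend on an unsourced input, particularly for the primary endpoint and when Potential Benefits looks ahead to a larger, rigorous trial. The FiO2 steps strengthen it. At an assumed PaO2 of 60, going from 36% to 40% moves the ratio by 60/0.36 − 60/0.40 = 16.7. If 5 of 30 patients shift one such step in the same direction and nobody else changes, the SD is already 16.7 × √(5 × 25/(30 × 29)) = 6.3. The remedy would be one paragraph.

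Part of this stands. The 6 is unsupported and may well be optimistic, and 51 should not be reused without a proper SD. What does not stand is the step to a defect in this plan. The document gives no SD of change. The background spread is cross-sectional, from ventilated patients, with an undefined ± and no correlation. The oxygen-step and room-air cases are constructed. A table at SD 8, 10 and 20 would put several unsourced values in place of one. The plan already labels its inputs as assumptions and disclaims adequate power. A later trial can take its SD from this one.

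**Conclusion.** No change is needed. The plan omits a source for the SD, but no stated size or power is shown to be wrong: 51 and 80% both reproduce, and the 30-patient sentence is true for any difference and SD whose ratio is 0.833. What is true is narrower. Those figures mean 5 mmHg only near SD 6; the power stays within 2 points of 80% for SDs of 5.74–6.04 (51 patients) and 5.79–6.19 (30 patients). At an assumed SD of 10 the chance with 30 patients is 0.50.

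No decision in the trial turns on this. The 30 was set for feasibility and safety, no confirmatory test is claimed, and the reported intervals will reflect the observed SD, with an 80% half-width of about 0.51 × SD if all 30 contribute. Missing day 7 values would widen it, and the interval would show that too.

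The conclusion rests on reading the paragraph as the plan words it, as an illustration with stated assumptions. It would differ if the 30 had been derived from the SD, or if the result were to be judged by a test powered on it.

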- 3) To assess the effect of treprostinil inhalation on oxygenation in patients with acute hypoxic respiratory failure with, or at risk for, development of ARDS
- 4) To assess the effect of treprostinil inhalation on various biomarkers thought to be related to the pathogenesis and/or clinical course of ARDS.

We propose a proof of concept, double blinded, placebo controlled study of inhaled treprostinil for patients with "at-risk" or early ARDS. Early, or pre-ARDS will be defined as acute hypoxemia and unilateral pulmonary infiltrates in patients presenting with conditions that are conducive to ARDS (e.g. pneumonia, sepsis, aspiration, trauma) but do not yet meet criteria for ARDS: require mechanical ventilation, bilateral infiltrates on CXR, and PaO_2/FiO_2 ratio < 300. The primary outcome will be PaO_2/FiO_2 ratio. We will also measure other physiologic and clinical outcomes and levels of inflammatory and pro-fibrotic biomarkers. This exploratory initial study will enroll 30 patients to assess feasibility and safety in this population.

Hypothesis:

- 1. Treprostinil inhalation is safe at planned dose titration in patients with acute hypoxemic respiratory failure
- 2. Treprostinil will improve oxygenation and other secondary outcomes related to mechanical ventilation initiation and duration, as well as exhibit effects on ARDS-related pro-inflammatory and pro-fibrotic biomarkers.

Study Design:

- 1) Single Center, proof of concept, 2:1 active drug to placebo controlled, double-blinded
- 2) Target of 30 patients enrolled
- 3) Patients will be randomized to receive either treprostinil or saline inhalation placebo
- 4) Patients will be followed to hospital discharge or day 28, whichever comes first. Those discharged prior to day 28 will be assumed free of mechanical ventilation and alive unless readmitted in that period. This will be confirmed by phone.

Sample Size/Interim Monitoring:

1) This is primarily a feasibility, safety and proof of concept trial.

Version: 02-09-2018

- 2) The primary endpoint is Change in PaO₂/FiO₂ ratio from Study Day 0 to 2, 7
- 3) Trial progress will be monitored by an independent Data and Safety Monitoring Board to determine if the study should stop for safety reasons. The first interim review will occur6 months following enrollment of the first patient or after the first 15 patients (which-ever occurs first) have been enrolled.

Inclusion Criteria:

- 1) Adults age 18-80 years.

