APPENDIX 2:

Schedule of Events

Description of Event	Day	Day	Day	Day	Day	Day	Day	Day	Day	Day	Day	Day	Day	Day	Day	Day
Description of Event	0	1	2	3	4	5	6	7	8	9	10	11	12	13	14	28
Inclusion / Exclusion Review	х															
Informed Consent	х															
Screening QTc	х															
Randomization	х															
Physical Examination	х															
Background Assessments	х			and Adr alysis U				story, He	eight; Ge	nder, M	easured	Body W	eight (M	l IBW); Ty	pe of Ho	spital
Baseline Assessments**	availa	ble for t	his 24 ho	our perio	d, the va	alue clos	est to th	hour int e time of measur	f randon	nization	will be re	ecorded.	If no va	lues are	availabl	
** Scoring (APACHE II and LIPS Scores)	х															
** Vital Signs and PaO ₂ ,PCO ₂ , pH; SpO ₂	х															
Available Labs ** Serum AST, ALT	х															
Required: ABG; Albumin; Bilirubin; BUN; Creat; Glucose; HCT; HGB; K; Na; Plt; WBC	х															
** Vasopressor or Inotropes Use	х															
Reference Measurements++	on the	specifi	c variabl		til stoppi	ng of stu		orded us , whiche								
Fluid Intake / Output	х	Х	х	х	х	х	х	х	х	х	х	х				
++ Vital Signs	х	х	х	х	х	х	х	х	х	х	х	х				
Concomitant Medication Use	х	х	х	х	x	x	x	x	x	x	x	x				
(Including Nebulized and Inhaled Medications)	^	^	^	^	^	^	^	^	^	^	^	^				
Lung Injury Score (Chest x-ray)	х			х				х								Х
Modified Brussels Score	х	х	х	х	х	х	х	х	х	х	х	х	х	х	х	
Study Drug Administration	х	х	х	х	х	х	х	х	х	х	х	х				
Blood Pressure Assessments (On Study Day 00, blood pressure will be checked prior to Dose 1 and 30 minutes after; prior to Dose 3 and 30 minutes after; prior to Dose 5 and 30 minutes or after a different dose interval, if the study drug had to be maintained due to an adverse effect. Blood pressure measurements for Study Days 01 through 11 will be captured from the nursing flow-sheets.	х	x	х	х	x	x	x	х	х	x	x	x				
Peak / Trough Specimen Collection (Peak Specimen will be obtained 15min [+/-5min] after Dose 1 on Day 3) (Trough Specimen will be obtained just prior to Dose 2 on Day 3)				х												

Biomarkers Specimen Collection	x			х				х						
(** Baseline specimen collection is prior to study drug administration)	^			^				^						
PaO ₂ / FiO ₂ Ratio (If the subject is still hospitalized)	х		Х					х						
SpO ₂ / FiO ₂ Ratio	х	х	х	х	х	х	х	х	х	х	х	х		Х
SCVO ₂ (if central venous catheter is in place)	х	х	х	х		х		х						
CVP (if central venous catheter is in place)	Х	х	х	х										

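### The stated 80% chance for 30 participants assumes that all 30 have a PaO₂/FiO₂ value and an unadjusted t test; no day is named and no allowance is made for missing Day 7 values

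*Combined protocol and SAP*

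**What the plan says.** The Sample size calculation section gives its basis as follows: "Sample size calculations are based on simple t tests". It assumes a change in P/F "ratio of 15 in the intervention group and 10 in controls" and "a standard deviation of 6 (effect size of 0.833"). It first finds that 34 + 17 patients would be needed for 80% power at the two-sided 5% level and concedes that the trial will not reach that number. It then states what the trial as designed can do: "The planned sample size of 30 total participants has 80% power". Power here means the chance that the two-sided 80% interval for the treatment difference lies wholly above 0, given that effect size. No day is named and missing values are not mentioned.

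Other sections bear on how many patients will have a value:

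- **Study Design:** "Single Center, proof of concept, 2:1 active drug to placebo controlled, double-blinded", with a target of 30 enrolled.
- **Primary Endpoint:** change in P/F from Day 0 to Days 2 and 7.
- **Appendix 2, Schedule of Events:** the P/F row carries the condition "If the subject is still hospitalized".
- **Treprostinil or Placebo Administration:** taper starts before Day 8 for patients who saturate above 90% on room air or who are expected to go home on oxygen, and study drug stops on the day of discharge home.
- **Completion of Study Drug Administration:** discharged patients receive a Day 28 telephone assessment.
- **Efficacy:** the primary analysis is an ANCOVA adjusted for baseline. A repeated-measures model (MMRM) is to be explored as support "if a number of patients do not have a day 7 assessment".

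**The concern.** The power statement treats 30 enrolled patients as 30 patients with a P/F value. The plan takes this measurement only from inpatients, in a population it expects may go home within the dosing period, and a telephone call cannot replace an arterial blood gas. The efficacy section makes provision for missing Day 7 values; the sample size section does not.

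This sentence is the only power statement made for the trial at its actual size. The efficacy section reports 80% intervals at both days as preliminary evidence of efficacy. A reader who meets a Day 7 interval that includes 0 would judge it against a stated 80% chance of success. If the real chance was clearly lower, such a result counts less against the drug than it appears to, which matters for the decision on a larger trial.

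**Working it through.** **Inputs (Sample size calculation; allocation from Study Design).** Difference 15 − 10 = 5; SD 6; d = 5/6 = 0.833; two-sided 80% interval; 2:1 allocation, so 30 patients are 20 + 10.

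**Formula.** The lower limit of a two-sided 80% interval exceeds 0 when the t statistic exceeds the 90th percentile of t on n₁ + n₂ − 2 degrees of freedom. The chance of this is

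1 − F(t₀.₉₀; df, λ), with λ = d / √(1/n₁ + 1/n₂),

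where F is the noncentral t distribution function.

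**Step 1: the plan's figure.** For 20 + 10, √(1/20 + 1/10) = √0.15 = 0.387, λ = 0.833/0.387 = 2.152, df = 28 and t₀.₉₀ = 1.313. The chance is **0.799** (normal approximation 0.808), which reproduces the stated 80%. Other readings do not: a one-sided 20% level gives 0.90, and 15 + 15 gives 0.83. The stated figure is therefore the 2:1, unadjusted t-test value with all 30 analysed.

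**Step 2: fewer evaluable patients, same d and same test.** The documents give no discharge or death rate by Day 7, so the 10% to 50% range of missing values is an assumption.

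| Evaluable | Split | Missing | λ | Chance |
|---|---|---|---|---|
| 30 | 20:10 | 0% | 2.152 | 0.799 |
| 29 | 19:10 | 3% | 2.133 | 0.793 |
| 28 | 19:9 | 7% | 2.059 | 0.772 |
| 27 | 18:9 | 10% | 2.041 | 0.766 |
| 24 | 16:8 | 20% | 1.925 | 0.728 |
| 21 | 14:7 | 30% | 1.800 | 0.684 |
| 18 | 12:6 | 40% | 1.667 | 0.634 |
| 15 | 10:5 | 50% | 1.521 | 0.576 |

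**Step 3: what the planned ANCOVA could recover.** If baseline has correlation r with the change, the residual SD is 6√(1 − r²), so λ is divided by √(1 − r²) and one more degree of freedom is lost. The documents give no r; the values below are assumed.

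- 27 evaluable: r = 0.3 gives λ = 2.041/√0.91 = 2.140 and a chance of 0.794; r = 0.5 gives 0.850.
- 24 evaluable: r = 0.5 gives λ = 1.925/√0.75 = 2.222 and a chance of 0.815.
- 21 evaluable: r = 0.6 gives λ = 1.800/√0.64 = 2.250 and a chance of 0.820.
- 15 evaluable: r = 0.7 gives λ = 1.521/√0.51 = 2.130 and a chance of 0.781, still short of 80%.

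**The case against.** The strongest reply is that nothing has been miscalculated, that the plan calls itself a feasibility and safety trial, and that no boundary or enrolment number depends on the 80%. The arithmetic is indeed right for 30 evaluable patients, and the consequence is modest. The disclaimer about low power, however, concerns the 5% significance test. The 80%-interval sentence follows it without qualification.

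Several stronger readings are tempting, but the documents do not support them:

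- **That any loss matters.** One lost treated patient takes 0.799 to 0.793. The plan's own 34 + 17 calculation, labelled 80%, has an exact t-test power of 0.785, so a shift of that order is within its rounding.
- **That the plan predicts a known shortfall at Day 7.** The efficacy wording is conditional, and no discharge or death rate is given.
- **That the 80% fails whatever Day 7 analysis is used.** The primary analysis is a baseline-adjusted ANCOVA. With 27 or 24 evaluable patients it could hold the chance near 80% at a moderate correlation. The stated figure cannot claim this gain, since it rests on t tests and gives no correlation. The MMRM is only exploratory.
- **That the figure is safe for Day 2 and only for Day 2.** The hospitalization condition covers the whole P/F row, Day 2 included. Fewer patients should have left by then, but that is a matter of degree.
- **That the DSMB would be misled.** The data listed for the DSMB are enrolment and safety; no P/F interval is among them.

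**Conclusion.** The concern holds in a limited form. The 80% is correct on two conditions that the sample size section does not spell out as such: every enrolled patient has a P/F value on the day in question, and the comparison is an unadjusted t test. The inpatient-only measurement, the provision for discharge before Day 8 and the provision for missing Day 7 values make the first condition unlikely at Day 7. On its own t-test basis the figure is then too high there, by an amount the documents do not give.

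Over the assumed range of 27 down to 15 evaluable patients, the unadjusted chance is 0.77 down to 0.58, that is, about 3 to 22 percentage points below 0.799. These values assume that the 2:1 split and the effect size of 0.833 still hold among patients who remain in hospital. Discharge is tied to oxygenation, so that subset may be selected. Counting evaluable patients does not address the possible bias. The point is an unstated assumption worth correcting in a non-confirmatory trial.

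**What to change.** Replace the 80%-interval sentence in the Sample size calculation section with text along these lines:

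> With all 30 patients evaluable (20:10), the chance that the two-sided 80% confidence interval lies above 0 at an effect size of 0.833 is about 80% by an unadjusted t test. This applies to Day 2 or Day 7 only with complete data on that day. P/F is taken only in hospital, so fewer patients are expected to be evaluable at Day 7. With an assumed 27, 24, 21 or 15 evaluable at 2:1 and the same effect size, the unadjusted t-test chance is about 77%, 73%, 68% or 58%. Adjustment for baseline in the planned ANCOVA may recover part of this loss, depending on the correlation of baseline with change, which is not known.

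The cost is a few sentences and a less favourable stated figure. Enrolment, procedures and the planned analyses stay as they are.
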